6.4.5.3 Analysis Following the Initiation of the COVID-19 Pandemic

In order to assess the impact of the COVID-19 pandemic on the primary endpoint, two additional analyses will be performed.

1) Exclusion of primary events after the start of the COVID-19 pandemic

The CEC reviewed all events occurring after the first reported case of COVID-19 in each participating country (generally the beginning of March, 2020). They assigned terms to each event, based on their clinical judgment, as to whether the event was (a) confirmed/related to COVID-19, (b) possibly related to COVID-19 or (c) not related to COVID-19. An exploratory analysis of the primary endpoint will be performed, excluding all events (a), and also excluding all events (a) or (b) from the definition of the primary endpoint as described below:

- a. The time from randomization to first occurrence of any component of the composite endpoint of CV death, resuscitated cardiac arrest, non-fatal MI or non-fatal stroke (primary endpoint), excluding adjudicated events confirmed/related to COVID-19, will be analysed using the same model as described in section 6.4.1.
- b. The time from randomization to first occurrence of any component of the composite endpoint of CV death, resuscitated cardiac arrest, non-fatal MI or non-fatal stroke (primary endpoint), excluding adjudicated events confirmed/related or possibly related to COVID-19, will be analysed using the same model as described in section 6.4.1.

2) Censoring after SAE diagnosed by investigators as due to COVID-19

Site Investigators were asked to report all serious adverse events related to COVID-19. Subjects in whom COVID-19-related SAEs occur will be censored at the time of the COVID-19-related SAE in an exploratory analysis of the primary endpoints as described below:

The time from randomization to first occurrence of any component of the composite endpoint of CV death, resuscitated cardiac arrest, non-fatal MI or non-fatal stroke (primary endpoint), censoring event-free subjects who experienced a COVID-19-related SAE (“COVID” included in the SAE term) at the date of first occurrence of COVID-19-related SAE, will be analysed using the same model as described in section 6.4.1.

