#### 7.1.1.4 Project-Specific Definition of SAEs

In this trial, positively adjudicated endpoints by the CEC (irrespective of investigators' causality) as well as those negatively adjudicated by the CEC and reported as unrelated to study medication by the investigators will be exempted from SAE reporting. However, all other events meeting SAE criteria will be reported as SAEs to the Sponsor.

Thus, the following events will not be reported as SAEs unless negatively adjudicated and considered study medication related by the investigator:

- Cardiovascular (CV) death
- Resuscitated cardiac arrest
- Non-fatal MI
- Non-fatal stroke
- Hospitalization with ACS (with ECG abnormalities)
- Hospitalization for ACS (with ECG abnormalities) requiring coronary revascularization
- Unanticipated coronary revascularization
- Hospitalization for new or worsening heart failure
- All-cause death

These events will be reported on the appropriate eCRF pages for the collection of information on endpoint events and forwarded to the CEC.

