2. STUDY DESCRIPTION

2.1 Study Design

This is a placebo-controlled, randomized, double-blind, parallel group, phase III multicenter study in subjects recently hospitalized for acute coronary syndrome (ACS) and with the appropriate genetic profile. Subjects provided informed consent before any study-specific procedures were performed. Subject enrollment was allowed to begin in the hospital and to continue following release from the hospital. Screening procedures were performed at the time of the index ACS event or anytime thereafter, with the condition that randomization had to occur within the mandated window (1-3 months after the index event). Subjects were assessed based on their medical history. Those who were likely to qualify underwent Cobas® ADCY9 Genotype CTA (Clinical Trial Assay) testing to evaluate genetic determination for the presence of the AA genotype at variant rs 1967309 in the ADCY9 gene. Those meeting the genetic testing criteria, all other inclusion criteria and none of the exclusion criteria were eligible for randomization. Eligible subjects had to be stabilized on statin and/or other medical therapy and had to complete all planned revascularization procedures prior to randomization. Subjects were randomized between 1 and 3 months from the index event. A total of 6149 eligible subjects in stable condition were randomized to 600 mg of dalcetrapib or placebo in a 1:1 ratio, stratified by region (Eastern Europe, Western Europe, North America, South America and other) and ACS index event (myocardial infarction [MI] or hospitalization for ACS [electrocardiogram changes without biomarkers]), to ensure equal number of subjects receiving active treatment and placebo in these strata. Subjects received study medication or placebo on a background of contemporary, evidence-based medical care for ACS. Subjects visit the clinic 1 and 6 months after randomization. Thereafter, visits are every 6 months for efficacy and safety assessments until completion of the trial. Phone assessments are performed 3 months after randomization and at the end of the study. Any subject prematurely discontinuing study medication and unable or unwilling to continue study visits, have phone assessments conducted every 6 months for the collection of study endpoints, with the exception of subjects who only agree to a final phone assessment. Due to the coronavirus pandemic of 2019 (COVID-19), to protect subject and study staff safety, it may not be possible for subjects to visit their clinic for study visits for some time and several alternatives for in-person study visits, and dispensing and returning study medication, are allowed as described in the study protocol.

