6. STATISTICAL METHODOLOGY

6.1 Sample Size

The sample size calculation is based on the primary endpoint. Under the following assumptions:

- an expected relative risk reduction of 22% and
- a statistical significance defined as a two-sided alpha of 0.05

the trial would have more than 85% power if it continues until at least 582 subjects experience a primary CEC adjudicated event in the combined treatment groups.

The total number of subjects to randomize, 6000, was chosen so that the expected number of subjects with an event is at least 582. It is based on the following assumptions, which were reviewed according to actual and planned recruitment rate:

- a 2.8-year recruitment period;
- a 1% yearly lost to follow-up rate; and

- a 7% event rate at 2 years following randomization in the placebo group.

A total of 6149 are actually randomized in the study.

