6.4.5.4 Analysis Based on Exposure to Study Treatment

Subjects who were off study treatment for an extended period of time may have a different risk profile as compared to the ITT population and two additional analyses will be performed to investigate the effect of exposure to study treatment.

- 1) Excluding events occurring 14 days after last dose of study treatment in subjects who discontinued study treatment prematurely

The time from randomization to first occurrence of any component of the composite endpoint of CV death, resuscitated cardiac arrest, non-fatal MI or non-fatal stroke (primary endpoint) will be calculated as number of days between randomization and event in subjects with an event and event-free subjects will be censored at the date they were last known to be event free (as for the primary analysis). However, in subjects who discontinued treatment prematurely (i.e. who reported a study treatment discontinuation on the *Treatment Inter/ Disc* Form of the eCRF), any event occurring 14 days or more after date of last dose will not count as an event. The analysis will be conducted on all randomized subjects (no subject excluded) using the same model as described in section 6.4.1.

- 2) Excluding subjects who discontinued study treatment prematurely and who had their first event at least 14 days after last dose of study treatment

The time from randomization to first occurrence of any component of the composite endpoint of CV death, resuscitated cardiac arrest, non-fatal MI or non-fatal stroke (primary endpoint) will be calculated as number of days between randomization and event in subjects with an event and event-free subjects will be censored at the date they were last known to be event free (as for the primary analysis). However, subjects who discontinued treatment prematurely (i.e. who reported a study treatment discontinuation on the *Treatment Inter/ Disc* Form of the eCRF) and who had a first event occurring 14 days or more after last dose will be excluded. The analysis will not be conducted on all randomized subjects since some would be excluded but it will use the same model as described in section 6.4.1.

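### SAP 6.4.5.3 item 2 states two different censoring rules after a COVID-19 SAE; the operative one, read as the SAP uses the term event-free, removes no primary event

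*SAP*

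**What the plan says.** SAP 6.4.5.3 plans two COVID-19 analyses of the primary endpoint. Item 1 drops events that the CEC labelled as COVID-related: first the confirmed/related ones, then also the possibly related ones. Item 2 works from investigator-reported SAEs. Its heading speaks of censoring after the SAE, and its lead sentence is unrestricted: "Subjects in whom COVID-19-related SAEs occur will be censored at the time of the COVID-19-related SAE". That sentence then points to the description below it. The description restricts the rule to "censoring event-free subjects who experienced a COVID-19-related SAE", with the censoring date set at the first such SAE. SAEs are picked by the string COVID in the SAE term.

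The next section, SAP 6.4.5.4, contrasts subjects with an event with the rest: "event-free subjects will be censored at the date they were last known to be event free (as for the primary analysis"). SAP 6.4.1 uses the term in the same way.

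On SAE reporting, Protocol 7.1.1.4 lists the endpoint events, including death, and says that "the following events will not be reported as SAEs unless negatively adjudicated and considered study medication related by the investigator".

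**The concern.** The two sentences of item 2 define different datasets. Take a subject with a COVID-19 SAE in month 30 and an MI in month 33. Under the lead sentence the subject is censored in month 30 and the MI does not count. Under the operative sentence, if event-free means having no primary event in the study, this subject is not event-free, so nothing is censored and the MI stays. Only a subject who has the SAE and never has an event loses follow-up.

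On that reading, whether a subject is censored at the SAE depends on what happens afterwards, which a time-to-event analysis should not allow. It also defeats the purpose of the item. The events that could carry a COVID-19 effect are all retained, so agreement with the primary result would be close to guaranteed and could be taken as evidence of robustness.

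**Working it through.** **Step 1: wording side by side.**
- The lead sentence of item 2 has no event-free restriction, but it defers to the sentence that follows.
- The operative sentence has the restriction. It does not say whether it applies at the SAE date or over the whole study, and it gives no rule for an event on the SAE date.
- SAP 6.4.1 and 6.4.5.4 use event-free for subjects without a primary event.
- Where the SAP means to discard later events, it says so. Item 1 of 6.4.5.4 states that events 14 days or more after the last dose do not count, and item 1 of 6.4.5.3 states that labelled events are excluded. Item 2 has no such clause.

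**Step 2: reproduce the plan's own figure.** SAP 6.1 gives "an expected relative risk reduction of 22"%, "a statistical significance defined as a two-sided alpha of 0.05", and states that "the trial would have more than 85% power if it continues until at least 582 subjects experience a primary CEC adjudicated event". Allocation is 1:1 (SAP 2.1). Schoenfeld's formula gives

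4 × (1.9600 + 1.0364)² / (ln 0.78)² = 4 × 8.978 / 0.06173 = 581.8, so 582 events.

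This matches, and the design inputs can be used.

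**Step 3: simulation set-up.**
- From the documents: 6149 subjects, 2.8-year accrual, 54 months in total, 1% yearly loss, hazard ratio 0.78, and a 7% placebo rate at 2 years, which is a yearly hazard of −ln(0.93)/2 = 0.0363.
- Assumed, because the documents do not give them: a pandemic window covering the last year; COVID-19 SAE risk in that window of 1% to 5%, equal or unequal by arm; primary-event hazard after the SAE multiplied by 1, 5 or 10; SAEs unrelated to baseline risk.
- 300 trials per scenario, unstratified Cox model. The primary analysis and both readings were run on the same data.

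**Step 4: results (mean hazard ratios).** The never-event reading removes 0 events in every scenario, by construction.

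| SAE risk, placebo / dalcetrapib | Hazard after SAE | Primary | Never-event reading | Event-free-at-SAE reading | Events removed, at-SAE reading |
|---|---|---|---|---|---|
| 1% / 1% | ×1 | 0.7862 | 0.7861 | 0.7861 | 0.9 |
| 3% / 3% | ×5 | 0.7804 | 0.7804 | 0.7807 | 12.8 |
| 5% / 5% | ×10 | 0.7825 | 0.7827 | 0.7814 | 39.8 |
| 2% / 5% | ×1 | 0.7841 | 0.7877 | 0.7840 | 2.8 |
| 2% / 5% | ×10 | 0.8098 | 0.8132 | 0.7792 | 27.0 |
| 5% / 2% | ×10 | 0.7586 | 0.7557 | 0.7856 | 29.2 |

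Absolute shift from the primary hazard ratio within a trial:
- Never-event reading, equal SAE risk: mean 0.0003 to 0.0007, largest 0.0036. Unequal risk: mean 0.003 to 0.004, largest 0.007.
- At-SAE reading, equal SAE risk: mean 0.002 to 0.013. Unequal risk: mean up to 0.031.

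Monte Carlo error of a mean hazard ratio is about 0.78 × (2/√582)/√300 = 0.0037, so 0.7792 and 0.7856 are both compatible with the true 0.78. Comparisons within a row use the same trials and are more precise.

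**Step 5: why the never-event reading moves the wrong way.** It leaves the events alone and removes person-time from the arm with more SAEs. Ignoring loss and events, mean follow-up is 4.5 − 2.8/2 = 3.1 years, and a censored subject loses about 0.5 years. With 2% / 5%, the fractions lost are 0.02 × 0.5/3.1 = 0.32% and 0.05 × 0.5/3.1 = 0.81%. The hazard ratio is multiplied by about 0.9968/0.9919 = 1.0049, a shift of 0.784 × 0.0049 = 0.0038. The simulation gave 0.0037 at ×1. The shift reflects lost person-time and not the effect of COVID-19 on events.

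**The case against.** The best defence is that item 2 already means event-free at the SAE. Its heading and lead sentence say so, the operative sentence is offered as the implementation of the lead sentence, and some such qualifier is needed because a subject whose primary event came first cannot be censored at a later SAE. SAP 6.4.5.2 also uses event-free for status at a point in time when it speaks of loss to follow-up. This stands as a plausible account of intent. It does not remove the problem: a programmer works from the operative sentence, the sections on either side favour the other meaning, and no clause says that later events are dropped.

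A reader might infer more than the documents support:
- That the rule, as defined, certainly removes no event. That holds on one of two available readings only.
- That it must return the primary hazard ratio exactly. Even on the never-event reading the ratio moves slightly, by up to about 0.007 here.
- That the text match on COVID causes the failure. On the never-event reading no event is removed however SAEs are found; on the other reading a text match could only misselect some SAEs. The documents do not show what terms were recorded.
- That COVID-related events go unexamined. Item 1 removes the CEC-labelled ones under either reading of item 2. It also covers COVID illness that presented as an endpoint and left no SAE because of the exemption in Protocol 7.1.1.4.

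Item 1 is still not a substitute for item 2. It removes events by the CEC's judgement of relatedness, while item 2 should also drop events after a COVID-19 SAE that the CEC judged unrelated.

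**Conclusion.** The concern holds as an internal inconsistency. Item 2 gives two censoring rules and does not choose between them. If the operative sentence is followed in the SAP's usual sense of event-free, censoring depends on the later outcome, 0 primary events are removed, and the analysis is nearly uninformative about COVID-19. With unequal SAE risk by arm it moves slightly away from the true effect.

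The size rests on assumed SAE risks, pandemic window and post-SAE hazards. With equal SAE risk by arm, the proper rule would itself shift the hazard ratio by only about 0.002 to 0.013 on average. The analysis is exploratory and, under SAP 6.4.6, descriptive. The primary test, its type I error and item 1 are untouched. It is worth correcting because the repair is cheap and the choice of rule should not be left until treatment is known.

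**What to change.** Replace the operative wording in SAP 6.4.5.3 item 2 with:

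> Subjects who are event-free at the date of their first COVID-19-related SAE are censored at that date, and primary events after that date are not counted, whatever the later outcome.

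Add one clause stating how a primary event on the same date as the SAE is handled.

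As a secondary step, select the SAEs from a list of coded COVID-19/SARS-CoV-2 terms, reviewed blind to treatment, instead of a text match alone. Keep the CEC relatedness labels in item 1 only, so that the two analyses remain separate checks.

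The cost is one sentence of SAP wording plus the same-date clause, and a short blinded term review. No new data are needed.

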6.4.5.4 Analysis Based on Exposure to Study Treatment

Subjects who were off study treatment for an extended period of time may have a different risk profile as compared to the ITT population and two additional analyses will be performed to investigate the effect of exposure to study treatment.

- 1) Excluding events occurring 14 days after last dose of study treatment in subjects who discontinued study treatment prematurely

The time from randomization to first occurrence of any component of the composite endpoint of CV death, resuscitated cardiac arrest, non-fatal MI or non-fatal stroke (primary endpoint) will be calculated as number of days between randomization and event in subjects with an event and event-free subjects will be censored at the date they were last known to be event free (as for the primary analysis). However, in subjects who discontinued treatment prematurely (i.e. who reported a study treatment discontinuation on the *Treatment Inter/ Disc* Form of the eCRF), any event occurring 14 days or more after date of last dose will not count as an event. The analysis will be conducted on all randomized subjects (no subject excluded) using the same model as described in section 6.4.1.

- 2) Excluding subjects who discontinued study treatment prematurely and who had their first event at least 14 days after last dose of study treatment

The time from randomization to first occurrence of any component of the composite endpoint of CV death, resuscitated cardiac arrest, non-fatal MI or non-fatal stroke (primary endpoint) will be calculated as number of days between randomization and event in subjects with an event and event-free subjects will be censored at the date they were last known to be event free (as for the primary analysis). However, subjects who discontinued treatment prematurely (i.e. who reported a study treatment discontinuation on the *Treatment Inter/ Disc* Form of the eCRF) and who had a first event occurring 14 days or more after last dose will be excluded. The analysis will not be conducted on all randomized subjects since some would be excluded but it will use the same model as described in section 6.4.1.

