#### 4.5 Criteria for Premature Study Medication Discontinuation

Based on extensive experience with dalcetrapib 600 mg/day in previous Phase III trials, dalcetrapib is well tolerated. However, if tolerability leads to considerations of study medication discontinuation, it is preferable to titrate the patient down to 300 mg/day (1 tablet per day instead of 2 tablets per day) at the investigator's discretion rather than discontinuing study medication. Any dose changes will be recorded in the eCRF. Subjects stopping study medication should be followed until the end of the study with the same procedures and not be withdrawn unless the subject refuses to give further information.

Additionally, for any subject prematurely discontinuing study medication, assessments will be conducted every 6 months for the collection of study endpoints and concomitant medications. Every effort must be made to obtain endpoint data through the duration of the trial, even if the patient discontinues study medication.

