6.3.6 Treatment Compliance

Accountability and subject compliance will be assessed by maintaining adequate drug dispensing and return records. Subjects will be asked to return all used and unused drug supply containers at each visit as a measure of compliance.

An overall compliance calculation will be performed using the study administration intake recorded. Compliance for the whole study is derived as follows:

$$\text{Compliance} = \frac{\text{\# days subject took study medication}}{\text{\# days in the study}} \times 100$$

days in the study = Date subject completed the study - date of randomization + 1.

Total time on study medication = Date of treatment last dose - date of treatment first dose + 1.

days subject took study medication (duration of treatment exposure) = Total time on study medication - the sum of all interruption durations for each record on the *Treatment Inter/ Disc* Form of the eCRF. It should be noted that only interruptions over 7 days are captured.

Subjects who died with no report of study drug discontinuation will be considered as discontinuing drug on date of death and date of treatment last dose will be imputed as date of death.

Compliance will be summarized by treatment arm using descriptive statistics.

Compliance will also be categorized as follow: < 80% or [80%-100%] and summarized accordingly using frequencies and percentages, by treatment arm, for the subjects of the ITT population.

Compliance results will be listed.

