6.4.6 Adjustment for multiplicity

Statistical testing of the primary and secondary endpoints will be done hierarchically to control the type 1 error rate at level 0.05. This will be done by testing the primary endpoint first and to test the secondary endpoints using the Hochberg procedure only if the primary analysis results in a significant treatment effect. Other analyses will be interpreted descriptively. The process is described below.

Primary Hypotheses:

The statistical hypotheses to be tested for the primary analysis are:

$$H_0: \lambda = 1 \text{ vs. } H_A: \lambda \neq 1$$

where λ is the HR for the time to occurrence of the primary endpoint for the dalcetrapib and placebo groups.

Secondary Hypotheses:

The statistical hypotheses to be tested for the secondary analyses are:

$$H_{0:S1}: \lambda_{S1} = 1 \text{ vs. } H_{A:S1}: \lambda_{S1} \neq 1$$

$$H_{0:S2}: \lambda_{S2} = 1 \text{ vs. } H_{A:S2}: \lambda_{S2} \neq 1$$

where

λ_{s1} is the HR for time to occurrence of the first secondary endpoint (CV death, resuscitated cardiac arrest, non-fatal MI, non-fatal stroke, hospitalization for ACS [with ECG abnormalities], or unanticipated coronary revascularization)

λ_{s2} is the HR for time to occurrence of the second secondary endpoint (CV death, resuscitated cardiac arrest, non-fatal MI, non-fatal stroke, or hospitalization for new or worsening heart failure)

Primary Analysis

Reject H_0 if p-value from the stratified Cox proportional hazards model is ≤ 0.05 .

Secondary Analyses

If H_0 is not rejected, the hypotheses for the secondary endpoints will not be formally tested. If H_0 is rejected, the following rules will be applied:

1. Order the p-values from the stratified Cox proportional hazards models of the secondary null hypotheses, $H_{0:s1}$ and $H_{0:s2}$, from largest to smallest.
2. If the largest p-value is ≤ 0.05 , reject both secondary null hypotheses.
3. If the largest p-value is > 0.05 and the smallest p-value is $\leq 0.05/2 = 0.025$, reject the secondary null hypotheses corresponding to the smallest p-value.
4. Otherwise, reject none of the secondary null hypotheses $H_{0:s1}$ and $H_{0:s2}$.

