6.5.1 Treatment Exposure

Duration of treatment exposure will be defined as number of days on treatment (computed as described in 6.3.6). Duration of treatment exposure will be summarized by treatment group using descriptive statistics. Duration of treatment exposure will also be categorized according to the following intervals (No exposure, 1-30, 31-182, 183-365, 366-730, 731-1095, and > 1095 days) and summarized accordingly using frequencies and percentages, by treatment group.

In addition, as a separate table, the number of subjects who had a permanent study treatment discontinuation will be summarized using frequencies and percentages, by treatment group.

Information on treatment exposure, study treatment interruption and study treatment discontinuation will also be listed.

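### Both exposure analyses in SAP 6.4.5.4 drop off-drug events but keep off-drug event-free time, so the hazard ratio favours whichever arm stops drug more

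*SAP*

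**What the plan says.** SAP 6.4.5.4 sets out two additional analyses of the primary composite, both using the Cox model of SAP 6.4.1, to investigate the effect of exposure to study treatment.

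- **Analysis 1** uses all randomized subjects. For those with a reported premature discontinuation, "any event occurring 14 days or more after date of last dose will not count as an event".
- **Analysis 2** drops subjects who discontinued prematurely and "who had a first event occurring 14 days or more after last dose will be excluded".
- **Censoring** is the same in both: "event-free subjects will be censored at the date they were last known to be event free (as for the primary analysis".

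Analysis 1 gives no explicit censoring date for a subject whose late event is discarded. Neither analysis censors at last dose + 14 days, and no other section does.

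Protocol 4.5 creates the off-drug follow-up: "Subjects stopping study medication should be followed until the end of the study with the same procedures". SAP 6.4.6 gives these analyses their status: "Other analyses will be interpreted descriptively". SAP 6.5.1 adds that "the number of subjects who had a permanent study treatment discontinuation will be summarized using frequencies and percentages, by treatment group".

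**The concern.** A Cox analysis needs the counted events and the time at risk to cover the same period. Here they do not. After last dose + 14 days a discontinuer can stay in the risk set for months or years while unable to contribute an event. Analysis 2 reaches nearly the same result by another route: it selects on outcome, deleting discontinuers who later had an event and keeping those who did not.

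If the arms have equal off-drug time, the distortion cancels in the HR. If one arm has materially more, its event rate is diluted more and its HR improves with no true effect. The section says it studies exposure, so a reader could take that shift for an on-treatment benefit. Unlike the sensitivity analyses in SAP 6.4.5.2, these do not depend on a significant primary result, so they will be reported even if the primary analysis misses.

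The plan uses matched censoring elsewhere. The second COVID-19 analysis in SAP 6.4.5.3 censors event-free subjects at the date of the COVID-19-related event, and Protocol 8.2.4.3 censors at the time of an interfering treatment or procedure.

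**Working it through.** **1. The plan's own figure.** SAP 6.1 assumes a 22% risk reduction (HR 0.78), "a statistical significance defined as a two-sided alpha of 0.05", and 85% power. With 1:1 allocation, events = 4(1.960 + 1.036)² / (ln 0.78)² = 35.91 / 0.0617 = 582. The stated target is reproduced.

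**2. Simulation inputs.**
- From the documents: 6149 subjects 1:1, accrual 2.8 years, total 54 months, loss 1% a year, 7% placebo event rate at 2 years.
- Hazard = −ln(0.93)/2 = 0.0363 a year, used in both arms (true HR 1.00).
- Mean follow-up without loss = 4.5 − 2.8/2 = 3.1 years.
- Assumed: exponential discontinuation, expressed as the cumulative percentage at 3.1 years. The documents give no rate.
- Cox model with treatment only, no strata, 3000 trials per setting.

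The mean ITT event count was 641. By formula, with λ = 0.0363 and loss hazard μ = 0.01005: 6149 × λ/(λ+μ) × (1 − mean of e^(−(λ+μ)T)), T uniform on 1.7 to 4.5 years, = 6149 × 0.783 × 0.133 ≈ 641.

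**3. Results**, as HR relative to ITT in the same trials:

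| Discontinuation, dalcetrapib v placebo | Analysis 1 | Analysis 2 | Censor at last dose + 14 days |
|---|---|---|---|
| 20% v 20% | 1.00 | 1.00 | 1.00 |
| 21% v 20% | 0.994 | 0.995 | 1.00 |
| 22% v 20% | 0.988 | 0.989 | 1.00 |
| 25% v 20% | 0.970 | 0.972 | 1.00 |
| 30% v 20% | 0.940 | 0.944 | 1.00 |
| 20% v 25% | 1.032 | 1.030 | 1.00 |

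Monte Carlo error of the log HR is 0.0005 to 0.0006. Analysis 1 is shown with a subject censored at the discarded event. Censoring at that subject's end of follow-up instead gives 0.969 at 25% v 20% and 0.938 at 30% v 20%.

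**4. Hand check at 25% v 20%.** Each arm expects 641/2 = 320.5 events. About 42 dalcetrapib and 33 placebo late events are discarded, leaving 278.5 and 287.5 (566 in all). Time at risk hardly changes, so the HR is about 278.5/287.5 = 0.969. The SE of log HR is 2/√566 = 0.084, and |ln 0.970| = 0.030, about one third of an SE.

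**5. False nominal results favouring dalcetrapib** (2.5% expected):

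| Setting | Analysis 1 | Analysis 2 | Last dose + 14 days | ITT |
|---|---|---|---|---|
| 25% v 20% | 5.0% | 4.8% | 2.5% | 2.3% |
| 30% v 20% | 11.6% | 10.4% | 3.2% | 3.1% |

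**6. Independent repeat**, 1.5 million subjects per arm, discontinuation at 3 years. At 25% v 20% both analyses give 0.97. At 30% v 20% they give 0.93–0.94 and 0.94. With a true HR of 0.78, 30% v 20% gives 0.73 in both, while censoring at last dose + 14 days gives 0.78. If the off-drug hazard doubles in both arms with an on-drug HR of 1.00, 30% v 20% gives ITT 1.05, analyses 1 and 2 0.94–0.95, and matched censoring 1.00. The two analyses then point the opposite way to ITT although the drug does nothing.

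**The case against.** **No decision depends on these analyses.** They are descriptive and outside the testing hierarchy, so a false-positive rate is only an illustration. The like-for-like contrast at 30% v 20% is 11.6% against 3.1% for ITT, not 2.5%. This stands, and it limits the severity.

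**The gap is hypothetical.** Neither document predicts unequal discontinuation. Protocol 4.5 describes the drug as well tolerated and prefers dose reduction to stopping. The by-arm table would reveal a gap. This also stands, but the table does not correct the HR.

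**The simulation leans high.** It reaches 641 events, while the trial stops near 582, and Protocol 4.4 and 5.5 foresee discontinuers who leave follow-up. With about 4.25 years and an assumed 25% of discontinuers ending follow-up at stopping, analyses 1 / 2 give 0.978 / 0.980 at 25% v 20% and 0.955 / 0.958 at 30% v 20%. With 50% assumed they give 0.987 / 0.988 and 0.971 / 0.973. The table above is therefore the upper range. The direction does not change.

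**Analysis 1 resembles a recognised estimand.** If discarded subjects stay to the end of follow-up, it keeps the risk set of a subdistribution-hazard analysis with stopping as the competing event. The SAP does not say so, and such an HR mixes the drug effect with the stopping rate, which is not the stated aim. The argument does not help analysis 2.

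**The remedy has its own bias** when stopping is related to risk. That is true and is quantified under the fix.

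**Conclusion.** The concern holds and should be fixed. As written, both analyses mismatch events and time at risk, and the HR moves towards the arm that stops drug more. The size is about 0.6% of the HR per percentage point of gap with near-complete off-drug follow-up, and less if many discontinuers leave follow-up. It is negligible at 1 point, about 3% at 5 points and about 6% at 10 points, and it reverses if placebo stops more. Confidence is high on mechanism and direction. The size rests on assumed discontinuation rates, exponential times, equal risk on and off drug in the main runs, and no strata. The ITT primary result, the Hochberg tests and the 582-event target are not touched.

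**What to change.** Replace the two analyses with one on-treatment analysis on all randomized subjects, using the SAP 6.4.1 model:

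- Count first primary events occurring less than 14 days after last dose in premature discontinuers. Treat all other subjects as in the primary analysis.
- Censor each premature discontinuer without such an event at the earlier of last dose + 14 days and the last known event-free date.
- For randomized subjects with no dose (the no-exposure class in SAP 6.5.1), use the randomization date in place of last dose.

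If the existing versions are kept, report them only beside this one and the by-arm discontinuation table, labelled as distorted when discontinuation is unequal. In that case, also state the censoring date for a discarded event in analysis 1.

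**Cost.** One paragraph and one changed censoring variable. The last-dose date is already used in SAP 6.3.6 ("Total time on study medication = Date of treatment last dose - date of treatment first dose + 1"), so no new data are needed. The counted events match the SAP's versions, except possibly for undosed subjects, whose number is unknown.

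**Limit.** The new censoring is unbiased only if stopping is unrelated to event risk. With an assumed gamma frailty of variance 1 driving both (1200 trials per setting, no true effect), it gives 0.978 at nominal 25% v 20% and 0.954 at 30% v 20%. Analyses 1 / 2 give 0.955 / 0.958 and 0.910 / 0.915. It then about halves the bias without removing it, so the result must stay supportive to ITT.
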